4. SUBJECT DISPOSITION

4.1. Participant Enrollment and Disposition

Key study dates (i.e., first participant screened, first participant randomized, last participant randomized, and last participant last visit for the clinical study report) will be provided.

4.1.1. Participant Enrollment

All necessary summaries on participant enrollment have been performed as part of the Week 48 analysis, and will not be repeated for the final analysis.

4.1.2. Participant Disposition

The summary of participant disposition will be provided by treatment group and overall for all randomized participants. This summary will include participants randomized, participants randomized but never treated, participants in the Safety Analysis Set, and participants in the FAS.

In addition, the number and percentage of the participants in the following categories will be summarized:

- Participants completing study drug in the randomized phase
- Participants prematurely discontinuing study drug in the randomized phase (with summary of reasons for discontinuing study drug in the randomized phase)
- Participants completing study in the randomized phase
- Participants prematurely discontinuing from study in the randomized phase (with summary of reasons for discontinuing from study in the randomized phase)
- Participants entering the OL extension phase
- Participants treated in the OL extension phase
- Participants completing study drug in the OL extension phase
- Prematurely discontinuing study drug in the OL extension phase (with summary of reasons for discontinuing study drug in the OL extension phase)
- Participants completing study in the OL extension phase
- Prematurely discontinuing from study in the OL extension phase (with summary of reasons for discontinuing from study in the OL extension phase)

The denominator for the percentages of participants in each category in the randomized phase, including "Participants entering the OL extension phase", will be the number of participants randomized and treated in the randomized phase. The denominator for the percentages of participants in each category in the OL extension phase will be the number of participants who were treated in OL extension phase.

No inferential statistics will be generated. A data listing of reasons for premature study drug/study discontinuation will be provided. Reasons for premature study drug/study discontinuation due to COVID-19 will also be provided in a separate listing.

4.2. Extent of Study Drug Exposure and Adherence

4.2.1. **Duration of Exposure to Study Drug**

Duration of exposure to study drug will be defined for the all B/F/TAF analysis. For the all B/F/TAF analysis, the terms "first dose date" and "last dose date" in the text below refer to the first dose date and last dose date defined for the all B/F/TAF phase analysis. Duration of exposure to study drug will be defined as (the last dose date – the first dose date + 1), regardless of temporary interruptions in study drug administration, and will be expressed in weeks using up to 1 decimal place (eg, 4.5 weeks).

Duration of exposure to study drug will be summarized using descriptive statistics (sample size, mean, SD, median, Q1, Q3, minimum, and maximum) and as the number and percentage of participants exposed for specified periods, eg, \geq 4 weeks (28 days), \geq 8 weeks (56 days), \geq 12 weeks (84 days), \geq 24 weeks (168 days), \geq 36 weeks (252 days), \geq 48 weeks (336 days), \geq 60 weeks (420 days), \geq 72 weeks (504 days), \geq 84 weeks (588 days), \geq 96 weeks (672 days), \geq 108 weeks (756 days), \geq 120 weeks (840 days), \geq 132 weeks (924 days), \geq 144 weeks (1008 days), etc.

Summaries will be provided by treatment group for participants in All B/F/TAF Analysis Set for the all B/F/TAF analysis, respectively. No inferential statistics will be provided.

Time to premature discontinuation of study drug will be analyzed by treatment group using the Kaplan-Meier (KM) method for the All B/F/TAF Analysis Set. No statistical comparisons will be made for the all B/F/TAF analysis. A plot of KM estimates for the time to premature discontinuation of study drug by treatment group will be generated for the All B/F/TAF analysis. Participants who completed study drug will be censored at the last dose data of the study.

4.2.2. Adherence to Study Drug Regimen

Adherence to study drug regimen will be defined for the all B/F/TAF analysis. For all B/F/TAF analysis, study drug adherence (for B/F/TAF) will be computed for both treatment groups as defined in Section 3.2. Study drug regimen adherence will be computed based on pill counts. The numbers of pills of study drug dispensed and returned are captured on study drug accountability eCRF.

Adherence (%) of study drug regimen will be calculated as follows:

Adherence (%) =
$$100 \times \frac{\text{Total No. of pills taken}}{\text{Total No. of pills prescribed}}$$

= $100 \times \frac{\sum \sum \text{No. of pills taken at each dispensing period}^{[1]}}{\sum \sum \text{No. of pills prescribed at each dispensing period}^{[2]}}$

- [1] Number of pills taken at a distinct dispensing period for a study drug is calculated as the minimum of (a) the daily number of pills prescribed for the study drug multiplied by the duration of treatment at the dispensing period, and (b) the number of pills taken for the study drug (number of pills dispensed minus the number of pills returned). Total number of pills taken is determined by summing the number of pills taken for each study drug contained in the study drug regimen from all evaluable dispensing periods.
- [2] Number of pills prescribed at a distinct dispensing period for a study drug is calculated as the daily number of pills prescribed for the study drug multiplied by the duration of treatment at the dispensing period. Total number of pills prescribed is determined by summing the number of pills prescribed for each study drug contained in the study drug regimen from all evaluable dispensing periods.

The duration of treatment at a dispensing period for a study drug is calculated as the minimum of (a) the last returned date of study drug at a dispensing period, (b) date of premature discontinuation of the study drug, and (c) next pill dispensing date of the study drug, minus dispensing date of the study drug.

The next pill dispensing date is the following dispensing date of the study drug regardless of the bottle return date.

For a record where the number of pills returned was missing (with "Yes" answered for "Was Bottle returned?" question), it is assumed the number of pills returned was zero. If the number of pills dispensed was missing or any study drug bottle was not returned or the bottle return status was unknown, then all records in that dispensing period for that study drug will be excluded from both denominator and numerator calculation.

Overall adherence will be calculated for the all B/F/TAF analysis. Overall adherence for the all B/F/TAF analysis will use all available data for participants who actually received B/F/TAF in the randomized phase, and data on or after the first dose date of extension B/F/TAF for participants who actually received DTG+F/TAF in the randomized phase and received at least 1 dose of B/F/TAF in the extension phase.

Descriptive statistics for adherence to a study drug regimen (sample size, mean, SD, median, Q1, Q3, minimum, and maximum) along with the number and percentage of participants belonging to adherence categories (eg, < 80%, $\ge 80\%$ to < 90%, $\ge 90\%$ to < 95%, $\ge 95\%$) will be provided by treatment group for participants who return at least 1 bottle of randomized study drug, and who have calculable adherence for the All B/F/TAF Analysis Set. No inferential statistics will be provided.

4.3. Protocol Deviations

A listing will be provided for all randomized participants who violated at least 1 inclusion or exclusion criterion. The listing will include the criteria not met. A listing of participants who received the wrong study drug will also be provided.

4.4. Assessment of COVID-19 Impact

This study was ongoing during the novel coronavirus (COVID-19) pandemic, which had an impact on the study conduct. Some participants were unable to attend onsite visits due to shelter in place guidelines, site closures, or other reasons. This section describes how special situations due to COVID-19 will be handled in the analysis. Data collection and determination of COVID-19 data are described in Appendix 5.

4.4.1. Study Drug or Study Discontinuation Due to COVID-19

A by-participant listing of reasons for premature study drug or study discontinuation due to COVID-19 will be provided if applicable.

4.4.2. Protocol Deviations Due to COVID-19

A by-participant listing will be provided for participants with important protocol deviations related to COVID-19 if applicable. A separate listing will be provided for participants with non-important protocol deviations related to COVID-19 if applicable.

4.4.3. Missed and Virtual Visits due to COVID-19

A by-participant listing of participants with missed or virtual visits due to COVID-19 will be provided by participant ID number in ascending order.

Information regarding missed or virtual visits due to COVID-19 will be collected as free text in the CRF comment fields. The determination of missed or virtual visits due to COVID-19 will be done using Natural Language Processing (NLP) to search the CRF comment fields. A detailed explanation of the algorithm is given in Appendix 5.

4.4.4. Adverse Events Due to COVID-19

Adverse events of COVID-19 will be included in analyses of AEs if applicable, which will be determined through COVID-19 SMQ narrow search. A by-participant listing of AEs of COVID-19 will be provided if applicable.

5. BASELINE CHARACTERISTICS

5.1. Demographics and Baseline Characteristics

Participant demographic data (eg, age, sex at birth, race, and ethnicity) and baseline characteristics (eg, body weight, height, and body mass index [BMI]) will be summarized by treatment group and overall using descriptive statistics (n, mean, SD, median, Q1, Q3, minimum, and maximum) for continuous data and by the number and percentage of participants for categorical data. The summaries of demographic data and baseline characteristics will be provided by treatment groups for participants in the All B/F/TAF Safety Analysis Set (noticing that the baseline for all B/F/TAF analysis will be adjusted based on first dose of B/F/TAF), respectively.

No statistical comparisons will be made for the All B/F/TAF analysis.

5.2. Baseline Disease Characteristics

5.2.1. HIV Baseline Characteristics

The following HIV baseline disease characteristics will be summarized by treatment group and overall using descriptive statistics for the All B/F/TAF analysis:

- HIV-1 RNA (log₁₀ copies/mL)
- HIV-1 RNA categories (copies/mL): (a) $\leq 100,000$, (b) > 100,000 to $\leq 400,000$, and (c) > 400,000
- CD4+ cell count (/µL)
- CD4+ cell count categories (/ μ L): (a) < 50, (b) \geq 50 to < 200, (c) \geq 200 to < 350, (d) \geq 350 to < 500, and (e) \geq 500
- CD4 percentage (%)
- Mode of infection (HIV risk factors)
- HIV disease status
- eGFR_{CG} (mL/min)

5.2.2. HBV Baseline Characteristics

The following HBV baseline disease characteristics will be summarized by treatment group and overall using descriptive statistics for the All B/F/TAF analysis:

- HBV DNA (log₁₀ IU/mL)
- HBV DNA categories (IU/mL): (a) $< 7 \log_{10}$, (b) $\ge 7 \log_{10}$ to $< 8 \log_{10}$, and (c) $\ge 8 \log_{10}$
- ALT (U/L)
- ALT category (ULN) based on central laboratory normal range: (a) ≤ 1, (b) > 1 to ≤ 5,
 (c) > 5 to ≤ 10, and (d) > 10
- ALT category (ULN) based on American Association for the Study of Liver Diseases (AASLD) normal range with the ULN as 25 U/L for female and 35 U/L for male: (a) ≤ 1, (b) > 1 to ≤ 5, (c) > 5 to ≤ 10, and (d) > 10
- Hepatitis B surface antigen status
- Hepatitis B surface antibody status
- Hepatitis B e-antigen status
- Hepatitis B e-antigen and HBV DNA stratum: (a) Positive and $\geq 8 \log_{10} IU/mL$, (b) Negative and $\geq 8 \log_{10} IU/mL$, (c) Positive and $\leq 8 \log_{10} IU/mL$, and (d) Negative and $\leq 8 \log_{10} IU/mL$
- Hepatitis B e-antibody status
- Hepatitis C antibody status
- HIV/HBV/HCV Coinfection (see definition in Section 8.1)
- HBV Genotype Group (A, B, C, D, E, F, etc.)
- Mode of infection (HBV risk factor)
- Years positive for HBV (Years since participant was first documented to be HBV positive)

No statistical comparisons will be made for the all B/F/TAF analysis.

5.3. Medical History

A listing of general medical history data will be provided.

General medical history data will be coded using the current version of Medical Dictionary for Regulatory Activities (MedDRA).

6. EFFICACY ANALYSES

All necessary summaries on the primary efficacy endpoint (at Week 48) and the secondary endpoints at Weeks 48 and 96 have been performed as part of the Week 48 CSR and Week 96 CSR, and will not be repeated for the final analysis.

6.1. Primary Efficacy Endpoints

6.1.1. Definition of the Primary Efficacy Endpoints

The primary efficacy endpoint is the proportion of participants with HIV-1 RNA < 50 copies/mL at Week 48 as determined by the US FDA-defined snapshot algorithm {U. S. Department of Health and Human Services 2015}. The proportions are expressed as percentages for presentation purposes.

The co-primary efficacy endpoint is the proportion of participants with plasma HBV DNA < 29 IU/mL at Week 48 as defined by Missing = Failure (M = F) approach.

The statistical analysis methods for the primary and co-primary efficacy endpoints were described in the Week 48 SAP and the analyses were performed in the Week 48 analysis, and will not be repeated for the final analysis.

6.2. Secondary Efficacy Endpoints

6.2.1. Definition of the Secondary Efficacy Endpoints

6.2.1.1. Secondary HIV Efficacy Endpoints

The secondary HIV efficacy endpoints include:

- The proportion of participants with HIV-1 RNA < 50 copies/mL at Weeks 96 as determined by the US FDA-defined snapshot algorithm
- The change from baseline in CD4+ cell count and CD4% at Weeks 48 and 96

6.2.1.2. Secondary HBV Efficacy Endpoints

The secondary HBV efficacy endpoints include:

- The proportion of participants with plasma HBV DNA < 29 IU/mL at Week 96
- The proportion of participants with ALT normalization at Weeks 48 and 96
- The proportion of participants with HBsAg loss at Weeks 48 and 96

Both baseline and postbaseline non-reactive HBV serology results will be imputed as negative, and reactive results will be imputed as positive.

The statistical analysis methods for the secondary efficacy endpoints at Weeks 48 and 96 (based on data included in the randomized phase analysis) were described in the previous interim analyses SAPs and the analyses were performed in the previous interim analyses.

6.3. Other Efficacy Endpoints for all B/F/TAF Analysis

6.3.1. Definition of the Other Efficacy Endpoint for all B/F/TAF analysis

The HIV efficacy endpoints for the all B/F/TAF analysis include:

- The proportion of participants with HIV-1 RNA < 50 copies/mL at Week 144 (OL Week 48) by M = E approach
- The change from baseline in CD4+ Cell Count and CD4 percentage (%) at Week 144 (OL Week 48)

The analyses for these efficacy endpoints above will be conducted based on the All B/F/TAF Full Analysis Set.

The HBV efficacy endpoints for the all B/F/TAF analysis include:

- The proportion of participants with plasma HBV DNA < 29 IU/mL at Week 144 (OL Week 48) by M = E approach
- The proportion of participants with ALT normalization at Week 144 (OL Week 48) by M = E approach
- The proportion of participants with normal ALT at Week 144 (OL Week 48) by M = E approach
- The proportion of participants with HBsAg loss at Week 144 (OL Week 48) by M = E approach

This is defined as HBsAg test result changes from HBsAg positive at baseline to HBsAg negative at a given postbaseline visit with baseline HBsAb negative or missing.

- The proportion of participants with HBsAg seroconversion to anti-HBs at Week 144 (OL Week 48) by M = E approach
 - This is defined as HBsAg loss and HBsAb test result changes from HBsAb negative or missing at baseline to HBsAb positive at a given postbaseline visit.
- The proportion of participants with HBeAg loss at Week 144 (OL Week 48) by M = E approach

This is defined as HBeAg test result changes from HBeAg positive at baseline to HBeAg negative at a given postbaseline visit with baseline HBeAb negative or missing.

• The proportion of participants with HBeAg seroconversion to HBeAb at Week 144 (OL Week 48) by M = E approach

This is defined as HBeAg loss and HBeAb test result changes from HBeAb negative or missing at baseline to HBeAb positive at a given postbaseline visit.

6.3.2. Analysis of Other Efficacy Endpoints for All B/F/TAF Analysis

6.3.2.1. Analysis of the Proportion of Participants with HIV-1 RNA < 50 copies/mL by Missing = Excluded Approaches

The proportion of participants with HIV-1 RNA < 50 copies/mL will be analyzed by M = E using the All B/F/TAF Full Analysis Set for the all B/F/TAF analysis.

In this approach, all missing data will be excluded in the computation of the percentages (ie, missing data points will be excluded from both the numerator and denominator in the computation). The denominator for percentages at a visit is the number of participants in the all B/F/TAF Full analysis set with nonmissing HIV-1 RNA value at that visit.

For the M = E analyses, the number and percentage of participants with HIV-1 RNA in the following categories will be summarized:

- < 50 copies/mL
 - -- < 20 copies/mL
 - < 20 copies/mL Not Detectable

 - < 20 copies/mL Detectable
 - -20 to < 50 copies/mL
- 50 to < 200 copies/mL
- 200 to < 400 copies/mL
- 400 to < 1000 copies/mL
- ≥ 1000 copies/mL

For all B/F/TAF analyses, the 95% CI for the proportion of participants with HIV-1 RNA < 50 copies/mL for a treatment group will be constructed using the Clopper-Pearson exact method.

For the M = E analysis, results will be summarized by treatment group for all visits through the end of study. No statistical comparison will be made for the all B/F/TAF analysis.

6.3.2.2. Analysis of CD4+ Cell Count and CD4%

The analysis of CD4 cell count will be based on on-treatment data (ie, up to 1 day after the last dose date of study drug) using the all B/F/TAF Full Analysis Set for the all B/F/TAF analysis.

The changes from baseline in CD4+ cell count at each visit will be summarized by treatment group using descriptive statistics. No statistical comparisons will be made for the all B/F/TAF analysis.

Similar analysis will be conducted for CD4% using the all B/F/TAF Analysis Full Set for the all B/F/TAF analysis.

In addition, the mean and 95% CI of change from baseline in CD4+ cell count over time while receiving B/F/TAF will be plotted.

6.3.2.3. Analysis of the Proportion of Participants with plasma HBV DNA < 29 IU/ by Missing = Excluded Approaches

The analysis of HBV DNA will be based on on-treatment data (ie, data collected up to 1 day after permanent discontinuation of study drug or all available data for participants who were still on study drug) for participants in the All B/F/TAF analysis.

In M = E approach, all missing data will be excluded in the computation of the percentages (ie, missing data points will be excluded from both the numerator and denominator in the computation). The denominator for percentages at a visit is the number of participants in the all B/F/TAF Full analysis set with nonmissing HBV DNA value at that visit.

For the M = E approach for HBV DNA, the number and percentage of participants with HBV DNA in the following categories will also be summarized by treatment group:

- < 29 IU/mL
 - -- < 20 IU/mL
 - < 20 IU/mL Not Detectable
 - < 20 IU/mL Detectable
 - $--- \ge 20 \text{ to} < 29 \text{ IU/mL}$
- > 29 IU/mL
 - $-- \ge 29 \text{ to} < 69 \text{ IU/mL}$
 - $-- \ge 69 \text{ IU/mL}$

For all B/F/TAF analyses, the 95% CI for the proportion of participants with HBV DNA < 29 IU/mL for a treatment group will be constructed using the Clopper-Pearson exact method.

For the M = E analysis, results will be summarized by treatment group for all visits through the end of study. No statistical comparison will be made for the all B/F/TAF analysis.

6.3.2.4. Analyses of the other HBV Efficacy Endpoints involving Proportions

All the other HBV efficacy endpoints involving proportions will be based on on-treatment data (ie, data collected up to 1 day after permanent discontinuation of study drug or all available data for participants who were still on study drug) and will be analyzed using M = E methods.

For the M = E analysis, results will be summarized by treatment group for all visits through the end of study. No statistical comparison will be made for the all B/F/TAF analysis.

The other HBV efficacy endpoints involving proportions will be assessed using all B/F/TAF FAS except the following:

- the proportion of participants with HBsAg seroconversion to anti-HBs by visit will be evaluated using all B/F/TAF serologically evaluable FAS for HBsAg loss/seroconversion.
- the proportion of participants with HBeAg seroconversion to anti-HBs by visit will be evaluated using all B/F/TAF serologically evaluable FAS for HBeAg loss/seroconversion.

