3.1.4. All B/F/TAF Serologically Evaluable Full Analysis Set

3.1.4.1. All B/F/TAF Serologically Evaluable Full Analysis Set for HBsAg Loss/Seroconversion

The All B/F/TAF Serologically Evaluable Full Analysis Set for HBsAg loss/seroconversion includes all participants who were in the All B/F/TAF Full Analysis Set, and with HBsAg positive and HBsAb negative or missing at baseline.

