3.1.4.2. All B/F/TAF Serologically Evaluable Full Analysis Set for HBeAg Loss/Seroconversion

The All B/F/TAF Serologically Evaluable Full Analysis Set for HBeAg loss/seroconversion includes all participants who were in the All B/F/TAF Full Analysis Set, and with HBeAg positive and HBeAb negative or missing at baseline.

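### SAP 6.3.2.4 exempts only seroconversion from the All B/F/TAF FAS, so the HBeAg loss denominator includes participants who cannot have the event

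*SAP*

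**What the plan says.** SAP 6.3.1 lists HBsAg loss, HBsAg seroconversion, HBeAg loss and HBeAg seroconversion as four separate proportions for the all-B/F/TAF analysis. HBeAg loss needs a positive baseline: "This is defined as HBeAg test result changes from HBeAg positive at baseline to HBeAg negative at a given postbaseline visit". The antibody, HBeAb, must also have been negative or missing beforehand. Seroconversion is loss plus the appearance of the matching antibody, so it is nested within loss.

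SAP 3.1.4.2 defines an evaluable set titled for HBeAg loss and seroconversion together. It "includes all participants who were in the All B/F/TAF Full Analysis Set, and with HBeAg positive and HBeAb negative or missing at baseline". SAP 3.1.4.1 does the same for the surface antigen: it "includes all participants who were in the All B/F/TAF Full Analysis Set, and with HBsAg positive and HBsAb negative or missing at baseline".

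SAP 6.3.2.4 then assigns populations: "The other HBV efficacy endpoints involving proportions will be assessed using all B/F/TAF FAS except the following". Two bullets follow, and each names seroconversion only. The second reads: "the proportion of participants with HBeAg seroconversion to anti-HBs by visit will be evaluated using all B/F/TAF serologically evaluable FAS". The word loss occurs in those bullets only inside the names of the sets. The same section says that these endpoints "will be analyzed using M = E methods".

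**The concern.** SAP 6.3.2.4 is the only place that assigns these endpoints to populations, and a programmer who follows it will compute HBeAg loss over the full analysis set. That set (SAP 3.1.2) has no serology condition, and HBeAg-negative participants are enrolled by design, since HBeAg status is a randomization stratum. A participant who is HBeAg negative at baseline and has a result at the visit is counted in the denominator without being at risk.

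Two consequences follow. The HBeAg loss percentage is diluted and cannot exceed the evaluable share of the set. And because seroconversion uses the smaller, correct denominator, two neighbouring rows can contradict each other, with seroconversion printed as more common than the loss that it requires.

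Only the denominator is at fault. The SAP 6.3.1 definition already keeps participants who were not positive at baseline out of the numerator.

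**Working it through.** **Text check.**

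1. Is HBeAg loss one of the endpoints that SAP 6.3.2.4 governs? Yes. It is a proportion listed in SAP 6.3.1 and is not HBV DNA, which has its own section (6.3.2.3).
2. Is it in the exceptions? No. Both name seroconversion only.
3. Does M = E remove participants who are not at risk? Not as the SAP describes it for HIV-1 RNA (6.3.2.1) and HBV DNA (6.3.2.3): "missing data points will be excluded from both the numerator and denominator in the computation". A negative HBeAg result is not missing.
4. Does another section place loss on the evaluable sets? No. The titles of 3.1.4.1 and 3.1.4.2 suggest it, but nothing assigns it.

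**Size.** The documents state no HBeAg loss rate, so there is no figure of the plan's to reproduce. Let N be the full-analysis-set participants with an HBeAg result at the visit, E those who are evaluable, L the losses, C the seroconversions, and s = E/N.

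- Printed loss = L/N. Evaluable loss = L/E. Their ratio is E/N = s, so the understatement is 1/s.
- Printed seroconversion = C/E. It exceeds printed loss when C/E > L/N, that is, when C/L > s.

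Inputs: s = 20% comes from the planning assumption in protocol 8.8 (20% HBeAg positive), taking every HBeAg-positive participant as evaluable. Because evaluability also needs HBeAb negative or missing, 20% is the upper bound at that mix, and 5-fold the lower bound on the understatement. The shares of 40%, 60% and 80% and the 30% evaluable loss rate are assumptions for illustration. N = 100 is a scale and stands for neither group.

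| s | E | L = 0.30 × E | Printed loss L/N | Evaluable loss L/E | Understatement 1/s | Smallest C with C/E > L/N |
|---|---|---|---|---|---|---|
| 20% | 20 | 6 | 6% | 30% | 5.0 | 2 (2/20 = 10.0%) |
| 40% | 40 | 12 | 12% | 30% | 2.5 | 5 (5/40 = 12.5%) |
| 60% | 60 | 18 | 18% | 30% | 1.67 | 11 (11/60 = 18.3%) |
| 80% | 80 | 24 | 24% | 30% | 1.25 | 20 (20/80 = 25.0%) |

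For HBsAg loss, if 90% to 100% of participants are evaluable (assumed), the understatement is 1/0.90 = 1.11 down to 1/1.00 = 1.00.

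**Switch group.** SAP 3.8.1 resets baseline at the first B/F/TAF dose for participants who started on DTG + F/TDF. Anyone who lost HBeAg during the blinded phase, and is still negative at the new baseline, is no longer evaluable but stays in the full analysis set. The dilution may therefore be larger there. The size of that group is not given.

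**The case against.** The strongest reply is that this is a drafting slip with an obvious intention. Both evaluable sets are titled for loss and seroconversion, and their baseline conditions match those in the SAP 6.3.1 loss definitions. SAP 6.3.2.4 also does not spell out what counts as missing for a change-from-baseline endpoint, so a programmer might treat loss as undefined for someone who was not positive and drop that person. It probably is a slip. But the exclusion is written nowhere, the two M = E denominators that the SAP does define depend only on a non-missing value at the visit, and the evaluable sets would be redundant if M = E did this work. The operative text points to the full analysis set.

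The second reply is that little depends on it, and this largely stands. The all-B/F/TAF analysis is descriptive, with no comparison between groups (SAP 3 and 6.3.2.4). HBeAg loss is not a protocol primary or secondary endpoint (protocol 8.1.2 and 8.1.3). The Week 48 and Week 96 results are already reported and are not repeated (SAP 6). Counts are shown beside percentages, and seroconversion is tabulated in the evaluable set, so a careful reader could largely recover the right rate.

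Third, the fold figures rest on a planning share and on assumed values, not on the enrolled population. That is so, and they are offered only as a range.

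Fourth, for HBsAg loss the full analysis set agrees with the protocol, which makes it the primary efficacy set (8.2.1.2.1) and adds no baseline serology condition in 8.5.2.2. The interim SAPs are not available, so consistency with the earlier reports cannot be checked. This is a fair caution. Against it, the SAP has defined a set named for HBsAg loss, and the numerical effect is probably small.

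**Conclusion.** The point holds. As written, HBeAg loss is computed over a population that includes participants who cannot have the event, in conflict with the set that SAP 3.1.4.2 defines for it. The printed rate is the evaluable rate times the evaluable share: understated at least 5-fold at the protocol's 20% planning share, and 1.25- to 2.5-fold at assumed shares of 80% down to 40%. The reading of the text is firm; the size is conditional, because the enrolled evaluable share is not given. The same gap affects HBsAg loss, probably by no more than about 1.1-fold if at least 90% are evaluable (assumed). No comparative or confirmatory result is affected. It should be fixed because the tables would otherwise carry a misleading percentage, and possibly a seroconversion rate above the loss rate.

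**What to change.** In SAP 6.3.2.4, name loss as well as seroconversion in both exceptions: HBeAg loss and HBeAg seroconversion in the 3.1.4.2 set, HBsAg loss and HBsAg seroconversion in the 3.1.4.1 set. If the Week 48 and Week 96 reports used a different denominator for HBsAg loss, say so in a table footnote.

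Two small corrections belong in the same place. The HBeAg bullet names the wrong antibody; SAP 6.3.1 has "HBeAg seroconversion to HBeAb". And the section should state that ALT normalization is assessed among participants with baseline ALT above the ULN, in line with the definition in protocol 8.5.2.2.

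The SAP carries electronic signatures dated April 2024. If it is final, SAP 1 gives the route: document the change in the CSR. The cost is a few words in two bullets and one clarifying line, since both serology sets already exist. The price is smaller denominators and so less precise percentages, mainly for HBeAg.
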